8.6 Incidences of common childhood infectious disease episodes

Incidence of episodes for each disease (number of episodes per child / total days of follow up per child) will be presented by intervention group. Incidence rate ratios (95% CI) will be calculated for each intervention group using the control group as the reference. Results will presented by intervention group (Table 5).

9 Hypothesis testing and statistical modelling

Risk of serious adverse events will be analysed using generalised linear modelling (log-binomial family). The Cox regression will be used in the analysis of mortality outcome. Differences in longitudinal prevalences of self-reported symptoms will be analysed and tested using least squares regression. Incidences of non-scheduled visits and morbidity episodes will be analysed using negative binomial regression.

The following is the list of the end-points and the types of modelling to be used for each endpoint:

End-p	oint	Statistical modelling		
i.	Risk of SAE	Log-binomial regression		
ii.	Longitudinal prevalence	Least squares regression		
iii.	Incidence of non-scheduled visits	Negative binomial regression		
iv.	Incidence of disease episodes	Negative binomial regression		

A set non-inferiority margin of 20% will used to test the hypotheses of no marked increase in the risk of SAEs, incidences of non-scheduled visits and morbidity episodes and prevalences of self-reported morbidity symptoms due to the intervention. An increased risk of >20% (risk ratio/incidence rate ratio >1.20) suggests a harmful effect associated with the intervention. The non-inferiority margin of 20% or an incidence difference of 20% has been used in previous

studies on nutritional supplementation and morbidity (Lemaire et al, 2011; Sazawal et al, 2006; Soofi et al, 2013).

The findings of the analysis will lead to one of the following four possible conclusions:

- i. If the upper bound of the 95% CI for the risk ratio/incidence rate ratio is <1.20, a conclusion of non-inferiority will be made.
- ii. If the lower bound of the 95% CI for the risk ratio/incidence rate ratio is >1.20, a conclusion of inferiority will be made.
- iii. If the upper bound of the 95% CI for the risk ratio/incidence rate ratio is <1.00, superiority will be confirmed (suggesting a beneficial effect).
- iv. If the upper bound of the 95% CI for the risk ratio/incidence rate ratio is >1.20 and lower bound is <1.20 we will interpret that the study has shown neither superiority nor inferiority. The findings will be considered inconclusive for target group inference.

The results will be plotted on a graph (Figure 3).

10 General notes on statistical methods

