12.2 Preparing anthropometric data for analysis

All the anthropometric measurements were completed in triplicate during each study visit. But for the analysis, the team will use the mean of the first two readings if they do not differ more than by a pre-specified tolerance limit. If they do, the third measurement will be compared with the first and second measurements and the pair of measurements that has smaller difference will be used to calculate the mean which will be used in analyses. If there are only one or two repeated measurements mean of those two will be used for the analyses.

The agreed tolerance limits between the first two measurements are:

- 1. length/height ≤ 0.5 cm
- 2. circumferences (head, MUAC) ≤ 0.5 cm
- 3. infant/child weight ≤ 0.1 kg
- 4. adult weight ≤ 0.1 kg
- 5. skinfold thickness $\leq 2.0 \text{ mm}$

The length, circumference and skinfold thickness measurements were recorded to last complete unit (mm). To account for the bias of always rounding the values a bit downwards, half a unit will be added to all length, circumference and skinfold thickness measurements prior to the analysis. This procedure is not done for weight measurements, since they were recorded accurately with electronic scales.

Missing growth values will be treated as missing, i.e. there will be no growth data imputation from the other data. Imputation is considered unreliable due to long time-interval between anthropometric measurements, at an age when growth faltering is common.

When measuring change in anthropometric values between two time intervals, the change will be treated as missing if there is a missing value in either of the respective time points.

12.3 Multiple comparisons

The study involves multiple objectives and therefore multiple sets of hypothesis. Statistically, the different sets of hypotheses are considered independent families of hypotheses. Statistical adjustment for multiple comparisons in one family of hypotheses does not need to consider the other families.

For efficacy analysis, each family consists of 5 hypotheses, each comparing an intervention group versus the control group. The Holm's adjustment method is used.

For safety analysis, it is preferable to err on the cautious side (Nauta, 2010). We began with testing the global null hypothesis of no difference between groups. If the global null hypothesis is rejected, raw P-values are used in the comparisons between intervention and control groups.

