Although nutritional supplementation is one of the recommended ways to combat child undernutrition, emerging evidence suggests that the supplements may be harmful in some instances. While a beneficial effect of nutrient supplementation on morbidity has been shown in some studies (Sharieff et al. 2006), big studies have shown that supplementation with multiple micronutrient powders or iron tablets may be associated with increased risk of common childhood infections (Sazawal et al, 2006, Soofi et al, 2013). Lipid-based nutrient supplement (LNS) is a product being tested for its potential in prevention of under nutrition and improving child growth outcomes in a randomised controlled trial in a rural Malawian population. It may be important to provide evidence of safety of LNS provision in settings where childhood infections are common. Previous studies on LNS have reported that the product appears to be safe but the evidence is still not conclusive. Such studies had either relatively short duration, i.e. 6 months or less, or did not have sufficient power because of small sample size (Dewey & Baldiviez, 2012). This study aims at assessing the safety of LNS when provided to healthy infants and young children for a period of 12 months. We will also explore any beneficial effects of LNS provision on morbidity, as an additional outcome.

3 Study objective

The main aim of this study is to assess the safety outcomes in children participating in the iLiNS-DOSE study in rural communities in Malawi. The outcomes are categorised as serious adverse events (SAE), non-scheduled visits, self-reported morbidity symptoms and self-reported disease episodes.

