8.4 Incidence of non-scheduled visits

The total number of non-scheduled visits will be tabulated by intervention group. The incidence of non-scheduled visits will be calculated as the number of non-scheduled visits / the total days of follow up in each group (Table 3). Incidence rate ratio (95% CI) will be calculated for each intervention group using the control group as reference.

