8.5 Longitudinal prevalences of self-reported common childhood morbidity symptoms

Longitudinal prevalence is defined as the proportion of days with the symptom in the study period. This will be calculated as total days of each reported morbidity symptom / total number

of days of follow up for each participant in each group to obtain group means. Geometric means ratio (95% CI) will be used to estimate and compare the mean longitudinal prevalences among the intervention and control groups using the control group as the reference. Results will presented by intervention group (Table 4).

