10.2 Preparing morbidity data for analysis

Using the weekly morbidity form (Form 18, table) morbidity variables were split to create a new dataset for each morbidity symptom. I created new variables for total days with symptoms and total follow up days in each dataset which were used to calculate prevalence of each morbidity symptom per child. Mean longitudinal prevalences for each group were derived from the individual prevalences. I created morbidity episodes from a combination of symptoms by merging the datasets of self-reported symptoms. Incidences in a group were calculated as the sum of events/episodes across individuals divided by sum of follow-up times across individuals. Preparation of these data was done using STATA and detailed steps taken in preparation of these data were recorded in a STATA do file

10.3 Confidence intervals

The confidence intervals at 95% level (95% CI) will be provided for all the outcomes. I will use log-binomial regression to derive the confidence intervals for SAE risk ratio, geometric means ratio to derive the confidence intervals for mean longitudinal prevalence and negative binomial regression to derive the confidence intervals for incidence of nonscheduled visit and self-reported disease episodes.

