

US Food and Drug Administration. Reporting Serious Problems to FDA. http://www.fda.gov/safety/medwatch/howtoreport/ucm053087.htm. (Accessed on 10th April 2014).

12 Legends to figures

Figure 1: Participant flow in CONSORT recommended format

Figure 2: Cumulative incidence curve for mortality

Figure 3: Graph of non-inferiority, comparing the risk ratios/incidence rate ratios of SAEs, non-scheduled events and care-giver reported morbidity between intervention and control group.

13 Tables

TABLE 1:

Baseline characteristics

Variable	Control	10g	20g	40g	Test
Number of participants	XXX	XXX	XXX	XXX	-
Mean (SD) age, months	xx.x (x.x)	xx.x (x.x)	xx.x (x.x)	xx.x (x.x)	ANOVA
Proportion of boys	xx.x%	xx.x%	xx.x%	XX.X%	χ^2
Mean (SD) HAZ-score	xx.x (x.x)	xx.x (x.x)	xx.x (x.x)	xx.x (x.x)	ANOVA
Mean (SD) WAZ-score	xx.x (x.x)	xx.x (x.x)	xx.x (x.x)	xx.x (x.x)	ANOVA
Mean (SD) WHZ-score	xx.x (x.x)	xx.x (x.x)	xx.x (x.x)	xx.x (x.x)	ANOVA
Mean (SD) haemoglobin, g/L	xxx (x.x)	xxx (x.x)	xxx (x.x)	xxx (x.x)	ANOVA
Proportion with anemia	xx.x%	XX.X%	XX.X%	XX.X%	χ^2
Proportion with iron deficiency	xx.x%	xx.x%	xx.x%	XX.X%	χ^2
Proportion with positive malaria RDT	xx.x%	XX.X%	XX.X%	XX.X%	χ^2

TABLE 2

Risk of SAEs by intervention group

	Results by study group				Comparison between the groups Risk ratio (95% CI)			
Variable	Control	10g LNS	20g LNS	40g LNS	10g LNS vs	20g LNS vs	40g LNS vs	
					control	control	control	
Number of participants	XXX	XXX	XXX	XXX	-	-	-	
Number of SAEs	XXX	XXX	XXX	XXX	-	-	-	
Number (%) of children who experienced any SAE	xxx (%)	xxx (%)	xxx (%)	xxx (%)	x.xx (xx to xx)	x.xx (xx to xx)	x.xx (xx to xx)	
Number (%) of children who experienced a hospitalization	xxx (%)	xxx (%)	xxx (%)	xxx (%)	x.xx (xx to xx)	x.xx (xx to xx)	x.xx (xx to xx)	
Number (%) of children who died	xxx (%)	xxx (%)	xxx (%)	xxx (%)	x.xx (xx to xx)	x.xx (xx to xx)	x.xx (xx to xx)	

Page 15 of 17

TABLE 3

Incidence of non-scheduled visits and clinical diagnoses, by intervention group

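### Appendix 8 calls superiority confirmed whenever an unadjusted 95% CI lies below 1.00, on up to 66 comparisons, although the plan states no superiority hypothesis and treats benefit as exploratory

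*SAP*

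**What the plan says.** Appendix 8 is framed as a safety analysis. Each of the four hypotheses in its section 4 says that an outcome is not markedly higher with LNS than without. Benefit appears once as an aim, in its section 2: "We will also explore any beneficial effects of LNS provision on morbidity, as an additional outcome".

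Section 9 sets a 20% non-inferiority margin and lists four possible conclusions, each read from a 95% CI. The third is: "If the upper bound of the 95% CI for the risk ratio/incidence rate ratio is <1.00, superiority will be confirmed (suggesting a beneficial effect"). The paragraph that introduces the margin covers SAEs, non-scheduled visits, disease episodes and the prevalences of reported symptoms.

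The intervals are ordinary ones. Section 10.3 says: "The confidence intervals at 95% level (95% CI) will be provided for all the outcomes". Sections 8.4 to 8.6 apply them to each intervention group against control. Section 10 covers software, data preparation, intervals, interaction and covariates. It has no part on multiple comparisons and does not refer to the main SAP on that subject.

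Main SAP section 12.3 has two regimes. On efficacy: "For efficacy analysis, each family consists of 5 hypotheses, each comparing an intervention group versus the control group", with Holm's method. On safety, a global test comes first, and raw P-values follow if it is rejected. It also says that adjustment in one family need not take account of other families. Main SAP section 4 treats analyses without predefined hypotheses as hypothesis-generating.

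**The concern.** The third conclusion turns an interval meant to rule out harm into a verdict of efficacy. Section 12.3 justifies lighter error control for safety by a wish to be cautious. That is a reason not to adjust a harm signal, but it does not extend to a claim of benefit.

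Appendix 8 uses neither regime of 12.3 and limits the rule to no particular outcome or dose. One symptom at one dose, with an upper bound just under 1.00, would qualify as confirmed superiority. Appendix 7, added on the same date as Appendix 8 (28.05.2014), already reports that no significant growth effect was seen. A confirmed morbidity benefit could then carry much of the trial's positive message.

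**Working it through.** **Setting the texts side by side**

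| Place | Status given to a benefit |
|---|---|
| Main SAP, section 4 | Without a predefined hypothesis: hypothesis-generating |
| Appendix 8, section 2 | Explored, as an additional outcome |
| Appendix 8, section 4 | No superiority hypothesis among the four |
| Appendix 8, section 9, third conclusion | Confirmed |

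The last row conflicts with the other three. This needs no calculation.

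**Counting the comparisons** (Appendix 8 table shells, each with 10 g, 20 g and 40 g against control)

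- Table 2: any SAE, hospitalization, death: 3 rows, risk ratios.
- Table 3: visits, gastroenteritis, respiratory infection, malaria, others: 5 rows. "Incidence rate ratio (95% CI) will be calculated for each intervention group using the control group as reference"
- Table 4: any illness and nine symptoms: 10 rows. "Geometric means ratio (95% CI) will be used to estimate and compare the mean longitudinal prevalences among the intervention and control groups"
- Table 5: gastroenteritis, respiratory infection, malaria, others: 4 rows. "Incidence rate ratios (95% CI) will be calculated for each intervention group using the control group as the reference"

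Total: (3 + 5 + 10 + 4) × 3 = 22 × 3 = 66. The third conclusion names only risk ratios and incidence rate ratios. Without Table 4 the count is (3 + 5 + 4) × 3 = 36. If the milk and milk-free arms stay separate (section 6), it is 22 × 5 = 110. The planned comparison of all LNS groups combined against control adds up to 22, making 66 + 22 = 88 with pooled doses.

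**Expected false results with no true effect.** A 95% interval lies wholly below 1.00 with probability 0.025.

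- 66 × 0.025 = 1.65
- 36 × 0.025 = 0.90
- 88 × 0.025 = 2.20
- 110 × 0.025 = 2.75

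**Chance of at least one.** The plan states no such figure, so there is none to reproduce. If all comparisons were independent it would be 1 − 0.975^66 = 0.81, or 1 − 0.975^36 = 0.60. They are not independent, because they share a control arm.

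The SAP gives 1932 infants. Equal allocation is an assumption: 1932 / 6 = 322, so the pooled groups are 322 (control), 322, 644 and 644. Two contrasts then correlate by (1/n₀) / √[(1/n₀ + 1/nᵢ)(1/n₀ + 1/nⱼ)]. This gives 0.58 for 10 g with either larger dose and 0.67 for 20 g with 40 g.

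A multivariate-normal simulation with these values and a common correlation between outcomes, counting any z below −1.96, gives:

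| Outcome correlation (assumed) | 66 comparisons | 36 comparisons | 66, Holm within each outcome |
|---|---|---|---|
| 0 | 0.73 | 0.51 | 0.37 |
| 0.3 | 0.53 | 0.39 | 0.27 |
| 0.5 | 0.41 | 0.32 | 0.21 |
| 0.7 | 0.30 | 0.24 | 0.14 |

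For 66 comparisons the probability falls to 0.50 at a correlation of about 0.35. With five separate arms (110 comparisons) it is 0.88, 0.68 and 0.55 at correlations 0, 0.3 and 0.5. Bonferroni over all 66 brings it to 0.023 or less.

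**The case against.** The case for leaving the rule alone has four parts.

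- **Section 12.3 may not require Holm here.** A reader might infer that it does. The document does not support that: Appendix 8 is a safety analysis, for which 12.3 prescribes a global test and then raw P-values. This part of the objection stands. What remains is that Appendix 8 has no global test either, and no link back to 12.3.
- **The family of 66 is not the SAP's own.** Section 12.3 declines adjustment across families, and an efficacy family is the set of arm-versus-control tests for one outcome. On that definition, and with uncorrelated outcomes, the excess is smaller: about 1 − (1 − 0.734)^(1/22) = 5.8% per outcome unadjusted, against 1 − (1 − 0.371)^(1/22) = 2.1% with Holm. This stands as a limit on the size of the departure from 12.3. It does not answer the word *confirmed*, which the rule makes available on every row.
- **A false benefit is not shown to be more likely than not.** A reader might infer that it is, barring strong correlation. The figures do not support this, since a moderate correlation of about 0.35 already brings the chance to one half. Several rows also overlap by construction: any SAE includes hospitalization and death, any illness includes the single symptoms, and the Table 5 episodes are built from reported symptoms. Sparse rows such as death may have less than the nominal error.
- **Table 4 may lie outside the rule.** Its effect measure is a geometric means ratio, which the rule does not name. The margin paragraph does include symptom prevalences, so the scope is ambiguous and both counts are shown.

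The rule's own parenthesis softens the verdict to a suggestion, and the tables report every row, so an isolated result would be seen in context. That lessens the consequence but leaves the contradiction in place.

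**Conclusion.** The concern holds as an unsupported confirmatory label. The third conclusion grants confirmed superiority from unadjusted intervals on up to 66 comparisons (36 on the literal reading). There is no superiority hypothesis behind it, no adjustment and no global test, and it runs against Appendix 8 section 2 and main SAP section 4.

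Under no true effect, the chance of at least one false confirmation runs from about 0.73 down to 0.30 for 66 comparisons, and from 0.51 down to 0.24 for 36, as the outcome correlation goes from 0 to 0.7. These figures rest on equal allocation, three pooled doses, a common outcome correlation that the document does not give, and a full 2.5% error in every row. The conflict between the passages depends on none of these.

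**What to change.** In the third conclusion of Appendix 8 section 9, drop the statement that superiority is confirmed. Say instead that the interval lies below 1.00 and suggests a possible benefit, and that the finding is exploratory, hypothesis-generating and not adjusted for multiple comparisons. State whether the rule covers the geometric means ratios of Table 4. Leave the harm and non-inferiority rules unchanged.

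If the sponsor wants a confirmatory benefit claim, it must name the outcome in advance and apply Holm over all arm-versus-control comparisons for that outcome: three if the milk and milk-free groups are pooled, five if not. The document does not say which outcome that should be. Longitudinal prevalence of any illness serves in section 6 only to decide on pooling, so it should not be taken as an already chosen lead outcome. Holm within every outcome would not be enough to call any row confirmed, because it leaves a chance of 0.37 to 0.14 across the 22 rows (correlations 0 to 0.7).

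The cost is a change of SAP wording. The downside is that unadjusted secondary morbidity outcomes can no longer support a confirmed benefit.

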The iLiNS-DOSE trial was designed to study the impact of a 12-month LNS provision to infants and young children on their growth, nutritional status and a number of other health outcomes. For this purpose, a total of 1932 infants were enrolled in rural Malawi, randomized to receive for 12 months either no supplement or one of five alternative LNS-preparations (six study groups in total), and intensely monitored for 12-months for a large number of outcomes. Key details of the trial have been recorded at the clinical trial registry at the National Institutes of Health (USA) (www.clinicaltrials.gov), under the registration number NCT00945698. A full trial protocol is available from the contact person to this document.

This document (called "the statistical analysis plan" or SAP) describes the study group's plan for data analysis, management, and storage. The SAP is designed to be evolving over time. Version 1.0 documents the details of the hypothesis testing and other analyses on primary and selected secondary outcomes. Subsequent versions of the SAP will give further details on the analyses and hypothesis testing of additional secondary outcome variables and exploratory analyses from the data.

3 Study objectives

The main aim of the trial is to assess the safety and impact of LNS supplementation on linear growth of infants and young children and to identify individual, household, and village-level characteristics that would modify the effects of LNS on child growth. A secondary aim is to similarly study the impact of LNS on various other (secondary) outcomes in the same target group. Finally, the trial aims to provide descriptive information on issues that might be necessary to facilitate future demand creation for LNS interventions.

The above aims have been broken down into the following first five objectives that were predefined in the trial protocol. The safety aim was not explicitly stated among the predefined objectives in the trial protocol, but was listed under the primary outcomes for analysis.

- 1. To determine the lowest daily dose of LNS that will promote linear growth among 6-18 months old infants in a rural Malawian community with poor food security. *This covers also the objective to study if ANY dose of LNS promotes linear growth among the target group.*

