The total number of serious adverse events (SAEs) will be presented by intervention group and SAE categorization, as indicated in Table 4. There will also be an analysis on the proportion of participants with at least one episode of SAE. For each of the intervention groups, the proportion and a relative risk (as compared to the control) will be presented as indicated in table 4. Fisher's exact test will be used to test the global null hypothesis of no differences between groups and the null hypothesis will be rejected if P<0.05. If the global null hypothesis is rejected, comparison between each intervention group and the control group will be conducted using log-binomial regression. Rate ratios (95% CI) for the incidence of any SAE will be calculated for each intervention group (as compared to the control group).

AE information was not collected after the participants had finished the intervention and completed the primary outcome study visit at 18 months of age.

Cumulative incidence curve for mortality will be presented graphically by intervention group as illustrated in Figure 3. The log-rank test will be used for testing global hypothesis and pair-wise comparisons. Hypothesis of equality of survivor functions is rejected if P<0.05. Hazard ratios and their confidence intervals will be estimated by the Cox regression model. The **sts** and **stcox** commands will be used.

12 General notes on statistical methods

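### A statistically significant but moderate excess of SAEs can end without a harm conclusion under both SAE rules (main SAP 11.5 and 12.3; Appendix 8, section 9)

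*SAP*

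**What the plan says.** **Main SAP.** Objective 6 (section 3) asks whether any LNS supplement raises the risk of serious adverse events. Section 4 bases conclusions on the main aim, which includes safety, on formal hypothesis testing. Section 11.5 then says "Fisher's exact test will be used to test the global null hypothesis of no differences between groups", at the 5% level. The next step is conditional: "If the global null hypothesis is rejected, comparison between each intervention group and the control group will be conducted using log-binomial regression". Section 12.3 introduces this with "For safety analysis, it is preferable to err on the cautious side" and repeats the condition: "If the global null hypothesis is rejected, raw P-values are used in the comparisons between intervention and control groups".

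Three other parts of the main SAP are not conditional:
- Section 11.5 presents each arm's proportion with an SAE and its relative risk against control.
- Section 12.4 gives confidence intervals whatever the tests show, for description.
- Table 4 has a raw p-value and a risk ratio with 95% CI for every arm.

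**Appendix 8.** It takes SAEs from the same source (Form 29, Q3.2) and sets a margin of 20%. Section 9 allows four conclusions, judged on the 95% CI of the ratio:
- (i) upper bound below 1.20: non-inferiority;
- (ii) lower bound above 1.20: inferiority;
- (iii) upper bound below 1.00: "superiority will be confirmed (suggesting a beneficial effect";
- (iv) upper bound "is >1.20 and lower bound is <1.20 we will interpret that the study has shown neither superiority nor inferiority".

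Section 6 of the appendix also plans a comparison of all LNS groups combined with control.

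**The concern.** Appendix 8 tests benefit against 1.00 and harm against 1.20. No permitted conclusion says that risk is increased. An interval of 1.10 to 2.21 is called inconclusive although it excludes no difference, and an interval wholly between 1.00 and 1.20 would be called only non-inferior.

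In the main SAP the first test is undirected and spread over six groups. It is not sensitive to a moderate excess shared by all LNS arms. If it does not reject, no formal LNS-control test follows, yet formal tests are what section 4 says the safety conclusion rests on.

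The two documents thus apply different rules to the same endpoint, and neither says which governs. What is at stake is the answer to objective 6: a real, statistically significant increase could be published without a conclusion that risk was raised.

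**Working it through.** The SAP gives no SAE rate and no power figure for SAEs, so there is no figure of its own to reproduce. What follows tests the rules under stated assumptions.

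**Inputs.** From the SAP: "a total of 1932 infants were enrolled in rural Malawi", six groups, 5% level, 95% intervals, limits 1.00 and 1.20. Assumed: equal groups, 1932 / 6 = 322 per arm; control SAE risk 5% to 20%; true risk ratios as given below.

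**1. Worked example.** Take 32/322 SAE cases in control and 50/322 in each of the five LNS arms (250/1610 pooled).

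RR = (50/322) / (32/322) = 1.56, and the same when pooled.

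SE(ln RR) = √(1/a − 1/n₁ + 1/c − 1/n₀); 95% CI = exp(ln RR ± 1.96 × SE).

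- One arm: √(1/50 − 1/322 + 1/32 − 1/322) = 0.212, CI 1.03 to 2.37 (pairwise Fisher P = 0.044).
- All LNS: √(1/250 − 1/1610 + 1/32 − 1/322) = 0.178, CI 1.10 to 2.21.
- Six-group Fisher test (Monte Carlo): P about 0.20.

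Main SAP: the global test does not reject, so no formal comparison follows. Appendix 8: both intervals straddle 1.20, so conclusion (iv) applies. Neither document concludes harm.

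**2. Width of the gap.** The smallest observed RR whose lower bound passes 1.00, against the smallest that passes 1.20:

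| Control risk | One arm v control | All LNS v control |
|---|---|---|
| 5% | 1.81 v 2.19 | 1.66 v 1.99 |
| 10% | 1.53 v 1.81 | 1.43 v 1.70 |
| 15% | 1.42 v 1.67 | 1.32 v 1.58 |
| 20% | 1.34 v 1.58 | 1.27 v 1.52 |

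An observed ratio between the two values is significantly above 1.00 and is labelled inconclusive.

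**3. How often both rules stay silent.** Simulated trials with a true RR of 1.5 in all five LNS arms. The six-group chi-square test (5 df) stands in for the 6×2 Fisher test. The main SAP is counted as flagging whenever the global test rejects, which is generous, because an arm-level test must still follow.

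| Control risk | Global test rejects | Pooled lower bound > 1.00 | Pooled lower bound > 1.20 | Above 1.00, flagged by neither |
|---|---|---|---|---|
| 5% | 18% | 33% | 11% | 16% |
| 10% | 41% | 66% | 22% | 27% |
| 15% | 65% | 87% | 34% | 23% |
| 20% | 84% | 96% | 48% | 13% |

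Check on the 10% row. The mean risk is (0.10 + 5 × 0.15)/6 = 0.1417. The noncentrality is 322 × [(0.0417)² + 5 × (0.0083)²] / (0.1417 × 0.8583) = 5.52, which gives 5-df power of 0.40.

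**4. Other patterns, 10% control risk.**

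| True RR | Global test rejects | Pooled lower bound > 1.00 |
|---|---|---|
| 2.0 in all LNS arms | 96% | over 99% |
| 2.0 in the two 40 g arms only | 99.9% | 47% |
| 2.0 in one arm only | 97% | 15% |
| 1.1 / 1.3 / 1.8 at 10 / 20 / 40 g | 88% | 59% |

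With RR 2.0 in all arms, about 4% of trials have a pooled interval above 1.00 that neither rule flags. With RR 1.5 in one arm only, the global test rejects in 48%, and about 24% of that arm's significant excesses escape both rules.

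**The case against.** Four points can be made for the plan.

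- **Straddling a margin is ordinarily inconclusive.** The hypothesis in Appendix 8 is that risk is not markedly higher, and main SAP 11.4 uses the same three-way logic. This stands for the non-inferiority claim. It does not explain why Appendix 8 adds a superiority conclusion at 1.00 for benefit and leaves out its mirror for harm.
- **Nothing is hidden.** Sections 11.5 and 12.4 and Table 4 show each arm's risk ratio and interval whatever the global test gives. The pairwise log-rank tests for mortality are not made conditional on the global test. Appendix 8 has no global gate. This stands: what is conditional is the formal test and the conclusion drawn from it. But Table 4's cells for raw pairwise p-values then conflict with the condition in 11.5 and 12.3.
- **The remark about caution in 12.3 may refer to raw instead of Holm-adjusted p-values.** That reading is possible, and the text does not settle it. The point here does not depend on it.
- **A shared RR of 1.5 is the pattern least favourable to a global test.** This stands. When a large excess is confined to the highest dose, the global test does far better than the pooled contrast, so pooled LNS v control should not become the lead SAE comparison in a dose trial.

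A reader might infer that neither rule ever flags a significant excess, or that the plan stops anyone looking at the comparisons. The documents do not support either reading: large excesses are flagged under both rules, and the estimates are always reported.

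**Conclusion.** The point holds for moderate excesses. Appendix 8 judges benefit and harm at different limits and has no conclusion for a lower bound above 1.00. The main SAP's condition can withhold the formal test from the same data. Under the shared RR of 1.5, between 13% and 27% of trials would show a significant pooled excess that neither rule calls harm, for control risks of 5% to 20%; the figure is 27% at 10%.

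These figures rest on equal arms and on assumed risks and effects, none of which the SAP gives. The wording gap itself needs no assumption. The case of an interval wholly between 1.00 and 1.20 is a defect of logic more than a practical risk for SAEs, because the SAE intervals at this sample size are too wide. Severity: should be fixed.

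**What to change.** - **Appendix 8, section 9.** Add a conclusion: if the lower bound exceeds 1.00, increased risk has been shown. Report it together with the margin result under (i) or (iv). Keep a lower bound above 1.20 as a marked increase.
- **Main SAP 11.5 and 12.3.** Report each arm's risk ratio, 95% CI and raw p-value whatever the global test gives, as Table 4 already provides. Keep the global test as one result among these. Put the all-LNS v control contrast, already planned in Appendix 8, beside the arm-level results and not ahead of them.
- **Both documents.** State that the same SAE rule governs the main SAP and Appendix 8.

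The cost is wording only: no new data and no change to the endpoint. The downside is a somewhat higher chance of a false safety signal among five unadjusted comparisons. The text should say so, and that p-values for SAEs are not adjusted for multiplicity.
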